5.5 Criteria for standard or fast withdrawal of immunosuppression (SWI versus FWI)

5.5.1 GVHD, MRD, and chimerism status must be assessed prior to each cycle and applied to risk stratification as above.

5.5.2 If the patient meets High-Risk criteria, then fast withdrawal of immunosuppression (FWI) will be initiated as early as Day +30.

5.5.3 If patient meets Standard-Risk criteria (or Low-Risk criteria for ALL patients), standard withdrawal of immunosuppression (SWI) will be initiated.

5.6 Schedule of standard and fast withdrawal of immunosuppression (SWI versus FWI)

5.6.1 Standard withdrawal of immunosuppression will be performed per institutional standard procedure. Suggested course of taper is over 10 weeks starting at day 30-50.

5.6.2 Fast withdrawal of immunosuppression will be performed per institutional standard procedure. Suggested course of taper is over 2-4 weeks starting at day 30-50.

5.7 Schedule of azacitidine administration

Azacitidine may be held or dose-adjusted based on the parameters below. If azacitidine is held > 6 weeks, the patient will remain on study but will be included in a separate analysis with regard to safety and efficacy.

5.7.1 Cytopenias prior to Cycle 1 require dose reductions as outlined below. Cytopenias following subsequent cycles require dose adjustments based on nadir counts as outlined in appendix 5.

- For platelets $< 30,000/\mu\text{L}$, 50% dose reduction is recommended.
- If platelet transfusion dependent, hold therapy until platelets $> 30,000/\mu\text{L}$.
- For neutrophils < 750 not responsive to GCSF, 50% dose reduction is recommended.
- For neutrophils < 500 not responsive to GCSF, hold therapy until toxicity improves.

5.7.2 Renal insufficiency:

- Creatinine $< 2X$ baseline: No dose adjustment is required.
- Creatinine 2-3X above baseline: Hold therapy until AKI resolves. Restart therapy at 50% dose reduction. If well-tolerated, full dose may be administered.

5.7.3 Hepatotoxicity:

- AST/ALT <5x ULN: No dose adjustment is required.
- AST/ALT 5-20x ULN: Hold therapy until transaminitis resolves. May consider 50% dose reduction and close monitoring.
- AST/ALT >20x ULN: Hold therapy until transaminitis resolves
- Total bilirubin 3-10x ULN: Hold therapy until resolution; may consider 50% dose reduction and close monitoring
- Total bilirubin >10x ULN: Hold therapy until resolution.

5.7.4 For other toxicities, repeat test twice weekly:

- Other laboratory abnormalities to be evaluated on a per-patient basis. Options include holding azacitidine until resolution, versus starting azacitidine at 50% dose reduction at the PI and treating physician's discretion.

5.7.5 Except for ALL patients classified as Low Risk, administration of azacitidine will commence during SWI or FWI if criteria are met (see section 6.2 for dose adjustment guidelines).

- Azacitidine will be given at a dose of 40mg /m² IV or SC daily for 4 days

5.7.6 Administration of azacitidine following SWI or FWI:

- PB and BM chimerism and MRD will be obtained as above and risk will be reassessed.
- No Intervention: For Low Risk ALL patients, azacitidine will be deferred. Patients will receive standard treatment and will be followed by BM every 3 months for 9-12 months.
- Azacitidine without DLI: Patients meeting Standard Risk criteria will receive azacitidine without DLI at a dose of 40mg/m² IV or SC x 4 days every 6 weeks. DLI should be considered for patients with resolved Grade 2 GHVD if pre- or post-transplant MRD is positive.
- Azacitidine with DLI: Patients meeting High Risk criteria, who also have available cells, will receive DLI in addition to azacitidine. Patients with history of Grade 2 GVHD (which has resolved) may also receive DLI if pre- or post-transplant MRD is positive at the discretion of the treating physician.
 - Administration of azacitidine following withdrawal of immunosuppression will commence (typically on a Monday) 2-8 weeks following *completion* of SWI/FWI (see section 6.2 for dose adjustments).
 - Azacitidine will be given at a dose of 40mg /m² IV or SC daily for 4 days every 6 weeks.
 - Escalating doses of DLI will be administered (typically on a Friday) within 5 days following the last dose of azacitidine every cycle (see section 5.8 for DLI schedule).
 - For patients with negative pre- and post-transplant MRD:
 - Once MDC resolves to FDC in both blood and bone marrow, DLI will be discontinued and patient will continue to receive azacitidine alone for a maximum of 7 cycles as tolerated.
 - If FDC is detected in blood, bone marrow chimerism must be obtained and confirmed to be mixed before proceeding with DLI.
- If DLI is administered without azacitidine during cycles 2 through 7, the subject should continue with all subsequent study assessments, but will be analyzed separately with regard to safety and efficacy.
- Cycles may be delayed for reasons such as toxicity, as per dose adjustment section 6.0.
- For all patients who receive azacitidine, a total of 7 cycles may be administered as tolerated.

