6.2 Azacitidine Toxicity

Guidelines for adjusting azacitidine dose administration are based on the Common Terminology Criteria for Adverse Events (CTCAE version 4.0) applied to patient reports, history and physical, and laboratory evaluations performed each cycle. Laboratory evaluations for toxicity will be performed the week prior to each cycle. Dose adjustments are as follows (28):

- 6.2.1 Development of drug-related grade 4 organ toxicity or severe infection:
 - Discontinuation of azacitidine

- 6.2.2 Hematologic toxicity:
 - Grade I-II toxicity: No dose adjustment is required.

- For platelets <30,000/uL on a stable transfusion regimen, 50% dose reduction is recommended.
- For platelets <15,000/uL, hold therapy until toxicity improves.
- For neutrophils <750 not responsive to GCSF, 50% dose reduction is recommended.
- For neutrophils <500 not responsive to GCSF, hold therapy until toxicity improves.
- See Appendix 5 for guidelines on subsequent dose adjustments based on nadir counts.

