6.2.4 Hepatotoxicity

- Grade I-II: No dose adjustment is required.
- Grade III (AST/ALT >5x ULN): Hold therapy until Grade III toxicity resolves if clearly related to azacitidine administration. Otherwise, consider 50% dose reduction and close monitoring.

6.2.5 For other toxicities, repeat test twice weekly:

- If abnormality resolves within 2 weeks, restart azacitidine at 50% dose reduction ($20\text{mg}/\text{m}^2$) to complete 4 doses. Proceed with DLI after 4th dose.
- If abnormality does not resolve after 2 weeks, hold azacitidine but proceed with DLI if no signs / symptoms of GVHD. Azacitidine 50% dose reduction should be used at start of next cycle even if lab abnormality returns to baseline.

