11.18 Classification of GVHD

To be classified as severe cGVHD, a minimum of 3 organs should be involved with stage 2 disease, or 2 organs with stage 3 disease. Please see Appendix 2 for a list of symptoms and staging. (For example: skin: 10 – 50% skin rash; Joint: mild joint contractures; and esophagus: dysphagia or odynophagia requiring dietary changes would qualify for severe cGVHD. Multiple symptoms within the same organ system should not be counted. Rash, sclerodermatous changes and dry flaky skin would all count as 1 organ/system involvement).

11.19 Hematopoietic toxicity:

- 11.4.4 Grade 3: ANC >500/microliter but < 1000/microliter for a duration of > 4 weeks. Platelets < 50,000/microliter but > 20,000/microliter for a duration of > 4 weeks.
- 11.4.5 Grade 4: neutrophils <500/microliter and/or platelets <20,000/microliter for a duration of > 4 weeks.
- 11.4.6 Grade 5: death due to bacterial or fungal infection or hemorrhage associated with hematopoietic toxicity.

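### Patients with azacitidine held over 6 weeks, or given DLI alone in cycles 2–7, go to a separate analysis, and section 8 does not say they stay in the primary proportions

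*Combined protocol and SAP*

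**What the plan says.** Two sentences in section 5.7 sort patients by what happens to their treatment after enrolment.

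- The opening of 5.7: "If azacitidine is held > 6 weeks, the patient will remain on study but will be included in a separate analysis" of safety and efficacy.
- The end of 5.7.6, for DLI given without azacitidine in cycles 2–7: "the subject should continue with all subsequent study assessments, but will be analyzed separately with regard to safety and efficacy". The next line adds: "Cycles may be delayed for reasons such as toxicity, as per dose adjustment section 6.0".

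Section 6.2 and Appendix 5 govern holds and discontinuation during treatment; 5.7.2–5.7.4 also list holds.

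- 6.2.1 discontinues azacitidine for: "Development of drug-related grade 4 organ toxicity or severe infection".
- 6.2.2: "For neutrophils <500 not responsive to GCSF, hold therapy until toxicity improves".
- 6.2.4: "Grade III (AST/ALT >5x ULN): Hold therapy until Grade III toxicity resolves if clearly related to azacitidine administration".
- 6.2.5, for other toxicities: "If abnormality does not resolve after 2 weeks, hold azacitidine but proceed with DLI if no signs / symptoms of GVHD".

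Section 11.19 defines haematopoietic toxicity, including: "Grade 4: neutrophils <500/microliter and/or platelets <20,000/microliter for a duration of > 4 weeks".

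Section 8.6.2 estimates two primary quantities as proportions with 95% CIs: the relapse rate, and the incidence of severe GVHD and Grade IV toxicity. It gives no denominator. No intention-to-treat, treated or safety set is defined anywhere in section 8. The protocol summary calls the study successful on relapse if the 2-year rate is below 25%.

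**The concern.** In a single-arm trial judged by proportions against fixed thresholds, the denominator is part of the result. The two sentences condition that denominator on a post-enrolment event that toxicity partly causes, and section 8 does not bring the patients back.

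On the removal reading, the primary relapse rate and the primary toxicity rate both describe patients selected by treatment course. A patient could leave the safety proportion because of the event that the proportion is meant to count. On the added-analysis reading there is no problem, but the plan does not say which reading applies. That choice should be fixed before results are seen.

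**Working it through.** **Inputs.** From 8.4.1: 67 patients, relapse 40% versus 25%, one-sided 0.05, 80% power. From 8.7.3: an assumed toxicity rate of 20%. From the protocol summary: the relapse criterion of below 25%. The number of patients meeting either trigger, and their outcomes, are not in the documents. Every moved count and event count below is an assumption.

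**1. The plan's own figure.** Normal approximation: n = [(1.645·√(0.40·0.60) + 0.842·√(0.25·0.75)) / 0.15]² = 60.9. With continuity correction: (n/4)·[1 + √(1 + 2/(0.15·n))]² = 67.4, which matches 67. An exact test at n = 67 rejects at 19 or fewer relapses, with level 3.24% and power 78.4%. Enrolment stops at 67, so there is no allowance for patients analysed elsewhere.

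**2. Which routes into the two groups overlap with a primary safety event?**

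- *Neutrophils (6.2.2).* If they stay below 500 throughout a hold of more than 6 weeks, they have been below 500 for more than 4 weeks. That is Grade 4 under 11.19. Appendix 5 B.3 limits some long count-driven holds, because it directs treatment if counts have not recovered by day 42. The two passages need reconciling.
- *Liver.* AST/ALT above 5× ULN is Grade III. It counts under 8.3.1 but not as Grade IV under 8.6.2. The 6.2.4 hold requires a clear relation to azacitidine; the 5.7.3 hold at 5–20× ULN has no such condition. These also need reconciling.
- *Other toxicities (6.2.5).* A patient managed exactly as written receives DLI without azacitidine and enters the 5.7.6 group.
- *GVHD.* 6.1 stops DLI once GVHD is suspected, so active GVHD does not lead to DLI alone.
- *Holds under 5.7.1* precede Cycle 1 and are not azacitidine toxicity.

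The overlap is real but partial.

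**3. Bounds on the toxicity proportion.** With e events in 67 and m patients moved, the result lies between (e − m)/(67 − m) and e/(67 − m). Take e = 13, so 13/67 = 19.4%, near the 20% of 8.7.3.

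- m = 5: 8/62 = 12.9% to 13/62 = 21.0%.
- m = 10: 3/57 = 5.3% to 13/57 = 22.8%.

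**4. Direction.** Let t be the true rate, f the fraction of event patients moved and g the fraction of the others moved. The apparent rate is t(1 − f) / [t(1 − f) + (1 − t)(1 − g)]. With t = 20%:

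- f = 50%, g = 25%: 0.10/0.70 = 14.3%.
- f = g = 50%: 0.10/0.50 = 20.0%.
- f = 25%, g = 50%: 0.15/0.55 = 27.3%.

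The sign depends on f and g, which are unknown.

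**5. Relapse against the 25% criterion.**

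- 16/67 = 23.9% (met) becomes 16/62 = 25.8% (not met) if 5 patients without relapse are moved.
- 20/67 = 29.9% (not met) becomes 15/62 = 24.2% (met) if 5 patients with relapse are moved.

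**6. Power.** The same exact test has 78.4% power at n = 67, 81.2% at n = 62 and about 76% at n = 57. Loss of power is not the argument.

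**The case against.** **Neither sentence says that patients are excluded.** This stands for 5.7, where inclusion in a separate analysis can mean an extra one. It is weaker for 5.7.6, where being analysed separately is most naturally removal. A reader might infer that the plan definitely drops both groups from the primary analysis. The text does not go that far; section 8 simply leaves the matter open.

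**Objective 2.1.1 names a combination of azacitidine and DLI, and 8.4.1 assumes azacitidine with or without DLI.** DLI alone is neither, so reporting it separately is defensible. That supports a supportive analysis. It does not settle the primary denominator, and it does not reach patients whose azacitidine was held.

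**Section 6.2.1.** A reader might infer that every patient with drug-related grade 4 organ toxicity leaves the safety proportion. The documents do not support this. 6.2.1 is a discontinuation, while 5.7 speaks of holds under the parameters listed beneath it. The plan does not say whether a discontinuation counts as a hold of more than 6 weeks.

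**Understated toxicity.** This is a tempting conclusion but it is not shown. The fractions moved are unknown, and step 4 gives results on both sides of the true rate. The relapse examples were chosen near 25% and move five patients with identical outcomes.

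**Consequences are limited.** The affected patients stay on study and are still analysed, and the 8.7 stopping counts state no exclusion. This stands. The question is only which number is primary.

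**Conclusion.** The point holds as an unresolved and potentially informative denominator, not as a demonstrated bias. 5.7 and 5.7.6 state a rule that separates patients by post-enrolment treatment course, toxicity partly drives that course, and section 8 names no set that keeps them in the 8.6.2 proportions. If the rule means removal, both primary estimates are conditioned on treatment course.

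The size is unknown. Under assumed counts, five moved patients are enough to take a 19.4% toxicity rate anywhere from 12.9% to 21.0%, and to reverse the relapse criterion in either direction. This should be fixed, because the correction is small and matters most if made before results are known.

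**What to change.** Reword the two sentences in 5.7 and 5.7.6 so that the separate analyses are described as supportive. Add one statement to 8.6: patients with azacitidine held more than 6 weeks, with azacitidine discontinued, or given DLI without azacitidine stay in the primary relapse and safety proportions.

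The cost is two reworded sentences and one new one. These patients already remain under study assessment, so no new data are needed. The downside is that the reported toxicity rate may be less favourable. No hold, dose or DLI rule changes.

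Three related matters are separate points and are not part of this change: the different toxicity definitions in 8.3 and 8.6.2, the undefined term *evaluable* in 8.4.1, and whether Low-Risk ALL patients count in the relapse denominator.

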5.8 Criteria for DLI

5.8.1 Deep Sequencing-MRD (ALL only)

- For Low-Risk ALL patients with Deep Sequencing-MRD negative on all measurements before and after transplant, azacitidine and DLI administration will not be given.
- Low-Risk ALL patients will undergo BM MRD and chimerism exams every 3 months for the first 9-12 months post-transplant. Intervention will be resumed if MRD becomes positive.

5.8.2 Mixed Chimerism

- Patients with persistent MDC following withdrawal of immunosuppression will receive DLI with the next cycle of azacitidine. Mixed chimerism of low purity should be repeated before proceeding with DLI and/or FWI in order to ensure mixed chimerism. If MDC persists after cycle 7, DLI may be administered without azacitidine after discussion with the study chair.
- Patients who revert to MDC on subsequent PB or BM testing will receive DLI with the next cycle of azacitidine.
- Patients with FDC are generally not eligible for further DLI except as described below.

5.8.3 Pre-Transplant MRD positive

- Patients with pre-transplant MRD $>10^{-5}$ are eligible to receive escalating DLI regardless of chimerism status if there is no active GVHD.
- If no active GVHD, DLI should continue until maximum DLI dose is achieved.

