Figure 1a: Schema for myeloid malignancies. Patients will be enrolled on study prior to Day +28. Chimerism from PB and BM as well as MRD will be assessed. Patients with Grade III-IV GVHD will not receive study immunomodulatory therapy. Patients meeting criteria for High-Risk designation will receive azacitidine followed by fast withdrawal of immunosuppression. Standard-Risk patients will receive azacitidine with standard withdrawal of immunosuppression. Risk assessment will be completed following withdrawal of immunosuppression, and patients will be assigned to receive azacitidine alone or azacitidine in combination with DLI based on current risk. Patients may receive up to 6 additional courses of azacitidine with or without DLI after withdrawal of immunosuppression; the addition of DLI will be guided by risk assessments done prior to each subsequent course.

Low Risk:

- Pre-Transplant Deep Sequencing (DS) MRD AND Post-Transplant DS- MRD negative ($<10^{-6}$)

Standard Risk:

- Active Grade I GVHD, OR
- Any history of >Grade II GVHD, OR
- Full Donor Chimerism AND Pre-HSCT MRD-neg AND Post-HSCT MRD-neg

High Risk:

- No GVHD or resolved Grade I GVHD, AND
- Mixed chimerism OR Pre-Tx MRD(+) OR Post-Tx MRD(+)

[figure not shown]

Figure 1b: Schema for acute lymphoblastic leukemia. Patients will be enrolled on study prior to Day +28. Chimerism from PB and BM as well as MRD (by conventional flow cytometry as well as deep sequencing when available) will be assessed. Patients with Grade III-IV GVHD will not receive study immunomodulatory therapy. Patients meeting criteria for High-Risk designation will receive azacitidine followed by fast withdrawal of immunosuppression. Standard-Risk patients will receive azacitidine with standard withdrawal of immunosuppression. Low-Risk patients will not receive study immunomodulatory intervention and will be treated per local SOP. Risk assessment will be completed following withdrawal of immunosuppression, and patients will be assigned to receive standard therapy, azacitidine alone, or azacitidine in combination with DLI based on current risk. Patients may receive up to 6 additional courses of azacitidine with or without DLI after withdrawal of immunosuppression; the addition of DLI will be guided by risk assessments done prior to each subsequent course.

Table of Contents

Section No.		Page No.
1.0	Background and Rationale.....	10

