3.0 Study Design and Eligibility Criteria

3.1 Study Design (see also Study Schema, page 3)

- 3.1.1 We propose a Phase II single-arm trial of azacitidine (IV or SC) in combination with escalating donor lymphocyte infusions (DLI). This study will be open to patients with ALL, AML, JMML, or MDS.
- 3.1.2 The first cycle of azacitidine will be administered during withdrawal of immunosuppression for patients not developing severe organ toxicity or Grade III-IV GVHD.
- 3.1.3 After the initial cycle during withdrawal of immunosuppression (duration is based on day 28 PB chimerism), azacitidine is given for 4 days in 6-week cycles (+/- 2 weeks) at a dose of 40 mg/m²/day.
- 3.1.4 For patients meeting High Risk criteria who have available cell product, DLI is given on day 5 of each cycle in escalating doses. Peripheral blood chimerism and MRD is assessed after week 4, prior to initiating the next cycle. BM chimerism and MRD is

obtained at regular intervals prior to specified cycles as per the study schedule. Patients will receive up to 7 cycles as tolerated.

3.1.5 Patients will be followed by laboratory monitoring and physician evaluation prior to each cycle. Weekly labs will be obtained and will include toxicity monitoring (CBC, LFTs, and electrolytes) and correlative studies, such as immunophenotype and T cell function by PHA. Patients will be followed for two years to study toxicity and GVHD outcomes as well as relapse incidence.

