5.3 Risk Stratification

- 5.3.1 Risk is evaluated and assigned prior to each azacitidine cycle based on clinical testing specific to that patient's disease.
- 5.3.2 For patients with MDS, any evidence of disease may be used to stratify the patient accordingly. In the absence of evidence of persistent disease, chimerism will be used to stratify the patient. MDS patients with no evidence of disease and 100% chimerism will be stratified as standard risk.
- 5.3.3 Peripheral blood disease assessment will be done as clinically indicated. Peripheral blood MRD by deep sequencing (if positive) may be used to risk-stratify ALL patients instead of bone marrow MRD. Any evidence of disease in peripheral blood for patients with AML/JMML or MDS will prompt BM evaluation as clinically indicated. In this instance, study treatment may continue after BM evaluation is complete.
- 5.3.4 Risk stratification criteria:
 - Low Risk
 - May only be applied to acute lymphoblastic leukemia patients
 - All of the following
 - Pre-transplant deep sequencing MRD negative, AND
 - All post-transplant deep sequencing MRD samples negative, AND
 - Any chimerism or GVHD status
 - ALL patients with negative deep-sequencing MRD pre- and post-transplant will be treated as low-risk regardless of chimerism
 - Standard Risk
 - Active Grade I GVHD, OR
 - Any history of Grade II (or higher) GVHD, OR
 - All of the following
 - Full Donor Chimerism AND
 - Pre-HSCT MRD $<10^{-5}$ (bone marrow) AND
 - Post-HSCT MRD $<10^{-5}$ (bone marrow), unless 3-fold increase is observed
 - High Risk
 - No active acute or chronic GVHD, AND
 - No history of Grade II (or higher) acute GVHD or chronic GVHD, AND

- Any of the following:
 - Mixed chimerism OR
 - Pre-HSCT MRD $> 1 \times 10^{-5}$ OR
 - Post-HSCT MRD at day 28 or later $\geq 10^{-5}$ once, OR
 - Post-HSCT MRD at day 28 or later $\geq 10^{-6}$ with ≥ 3 -fold increase on any subsequent measurement (need not be consecutive).
 - Post-HSCT MRD $< 1 \times 10^{-5}$ is treated as Standard Risk until a 3-fold increase is documented.

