5.8.4 Post-Transplant MRD positive

- For patients with persistent MRD post-transplant ($>1 \times 10^{-5}$ or 1×10^{-6} and increasing) and with no active GVHD, azacitidine and escalating doses of DLI should be administered.
- DLI should be escalated to maximum dose and administered while MRD remains positive. If MRD is positive after cycle 7, DLI may be administered with or without azacitidine after discussion with the study chair.

5.9 Intra-patient DLI dose escalation to be used on day 5 (following 4 days of azacitidine):

5.9.1 Mismatched related donor or any unrelated donor:

- 1st dose: 5×10^5 /kg -- 1×10^6 /kg of CD3+ cells
- 2nd dose: 1×10^6 /kg -- 1×10^7 /kg of CD3+ cells
- 3rd and all subsequent doses: 1×10^7 /kg -- 5×10^7 /kg of CD3+ cells

5.9.2 Matched related donor:

- 1st dose: 1×10^7 /kg of CD3+ cells
- 2nd and subsequent doses: 5×10^7 /kg of CD3+ cells

5.9.3 Peripheral blood chimerism will be repeated during or after week 4 of every cycle, and the next cycle will not be initiated until results are obtained.

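### Sections 5.8.3 and 5.8.4 make DLI depend only on the absence of active GVHD, while 5.3.4, 3.1.4 and 5.7.6 also exclude patients by GVHD history

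*Combined protocol and SAP*

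**What the plan says.** **Section 5.8, the DLI criteria.** Patients with pre-transplant MRD above the threshold "are eligible to receive escalating DLI regardless of chimerism status if there is no active GVHD" (5.8.3). The next line adds: "If no active GVHD, DLI should continue until maximum DLI dose is achieved". For persistent post-transplant MRD, 5.8.4 sets the MRD level and continues: "and with no active GVHD, azacitidine and escalating doses of DLI should be administered". Neither subsection mentions past GVHD or refers to the risk groups. Section 5.8.2, on mixed chimerism, states no GVHD condition. Nor does 5.4.2, which calls any patient with detectable host cells high risk.

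**Risk groups and allocation.** Section 5.3.4 requires a High Risk patient to have no active GVHD and also "No history of Grade II (or higher) acute GVHD or chronic GVHD, AND" one of the listed chimerism or MRD findings. One of its alternative routes into Standard Risk is "Any history of Grade II (or higher) GVHD, OR", whatever the MRD result. Section 3.1.4 allocates DLI by risk group: "For patients meeting High Risk criteria who have available cell product, DLI is given on day 5 of each cycle in escalating doses". Section 5.7.6 gives Standard Risk patients azacitidine without DLI and names one exception: after resolved Grade 2 GVHD with positive MRD, DLI is to be considered and may be given if the treating physician so decides. The legends to Figures 1a and 1b say that "the addition of DLI will be guided by risk assessments done prior to each subsequent course".

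**The concern.** GVHD is the main harm of DLI. Section 9.1 puts GVHD after withdrawal of immunosuppression and DLI at 50-65%, with about a 10% chance of dying from it. A site that opens 5.8, finds a child MRD-positive with no GVHD at that visit, and follows the text would give escalating donor T cells to a child whom 5.3.4 keeps out of the DLI group because of past GVHD. Another of the three sites, working from 5.3.4 and 5.7.6, would give the same child none.

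The choice also reaches the monitoring. Section 8.7.3 suspends enrollment and further DLI if severe acute GVHD or GVHD deaths among DLI recipients exceed published rates, so who counts as a legitimate recipient affects that rule.

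**Working it through.** The plan states no figure on this point, so the check is a comparison of rules followed by the dose arithmetic.

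**1. Rule comparison.** Take an MRD-positive child with no active GVHD and cells available, and vary only the GVHD history.

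| GVHD history | 5.3.4 / 3.1.4 / 5.7.6 | 5.8.3 (pre-transplant MRD) | 5.8.4 (persistent post-transplant MRD) | Agreement |
|---|---|---|---|---|
| None, or resolved Grade I acute | High Risk: DLI | Eligible | DLI should be given | Yes |
| Resolved Grade II acute | Not High Risk; DLI at physician discretion | Eligible, then should continue to maximum dose | DLI should be given | No: *may* against *should* |
| Resolved Grade III-IV acute | Standard Risk, outside the exception: no DLI | Eligible, then should continue | DLI should be given | No |
| Resolved chronic | Not High Risk, outside the exception: no DLI | Eligible, then should continue | DLI should be given | No |

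The chronic GVHD row reads the High Risk history criterion as excluding any past chronic GVHD. The schema supports this, because its High Risk box admits only patients with no GVHD or with resolved Grade I.

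**2. Number of infusions.** Table 1 has cycle 1 as azacitidine alone and cycles 2 to 7 as azacitidine with or without DLI, so at most 7 − 1 = 6 infusions fall within cycles.

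**3. CD3+ cells per kg, from the dose steps in 5.9.**

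Matched related donor (5.9.2):
- To the maximum level (5.8.3): 1 × 10^7 + 5 × 10^7 = 6 × 10^7, in 2 infusions.
- Six infusions (5.8.4): 1 × 10^7 + 5 × (5 × 10^7) = 2.6 × 10^8.

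Mismatched related or unrelated donor (5.9.1), using the ends of each dose range:
- To the maximum level, low end: 5 × 10^5 + 1 × 10^6 + 1 × 10^7 = 1.15 × 10^7, in 3 infusions.
- To the maximum level, high end: 1 × 10^6 + 1 × 10^7 + 5 × 10^7 = 6.1 × 10^7, in 3 infusions.
- Six infusions, low end: 5 × 10^5 + 1 × 10^6 + 4 × (1 × 10^7) = 4.15 × 10^7.
- Six infusions, high end: 1 × 10^6 + 1 × 10^7 + 4 × (5 × 10^7) = 2.11 × 10^8.

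Under the stricter rules the total is 0 for resolved Grade III-IV acute or chronic GVHD.

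The 5.8.3 totals assume that DLI ends with the first infusion at the top level. The six-infusion totals are ceilings within cycles 2 to 7. A child whose GVHD arose and resolved during those cycles has fewer infusions left. Beyond cycle 7 no number is stated: "If MRD is positive after cycle 7, DLI may be administered with or without azacitidine after discussion with the study chair".

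**The case against.** The strongest reply is that 5.8 was never meant to stand alone. Section 5.7.6 refers sites to 5.8 from its branch for DLI with azacitidine, which opens with the High Risk criteria, and 5.3.1 and 5.5.1 require risk to be assessed before every cycle. A site should therefore have applied the GVHD-history criteria before it reaches 5.8. On that view 5.8.3 and 5.8.4 only lift the bar on DLI for full donor chimeras at the end of 5.8.2. This is a fair reading and probably the intended one. It does not remove the conflict: 5.8 is headed as the criteria for DLI, never cites 5.3.4, and sets a GVHD condition that would add nothing for a patient already classed as High Risk.

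Three other texts point against DLI in these children, and none settles the matter.

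- The legends to Figures 1a and 1b withhold study immunomodulatory therapy from patients with Grade III-IV GVHD, and 3.1.2 limits the first azacitidine cycle similarly. Neither says whether resolved disease is covered. Section 5.3.4 places a history of Grade II or higher in Standard Risk, which does receive azacitidine. Neither text mentions chronic GVHD.
- Section 6.1 stops DLI and withdrawal of immunosuppression once GVHD is suspected, whatever the MRD result. It is silent on resuming after resolution.
- Appendix 3 bars DLI after acute GVHD above Grade II and ends DLI if GVHD follows an infusion. Its stated objective covers DLI given outside an investigational study, and 6.1 cites it only for toxicity management.

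A reader might infer that the protocol orders DLI for every MRD-positive child with past severe GVHD. It does not. The entry line of 5.8.3 says *eligible*; only its continuation line and 5.8.4 say *should*, and most of the protocol points the other way. A reader might also take the section 9.1 percentages as the risk of dosing after resolved GVHD. They are general figures for withdrawal of immunosuppression and DLI.

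**Conclusion.** The inconsistency is real and concerns safety and treatment assignment. It changes no sample size, power or error rate. The operative texts give different DLI instructions for MRD-positive children with resolved chronic GVHD, where no other text helps, and with resolved Grade III-IV acute GVHD, where the figure legends lean against DLI without deciding it. For resolved Grade 2, 5.8.4 turns the physician's choice in 5.7.6 into a direction.

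Per child, the difference is between no DLI and the ceilings worked out above, assuming cells are available. How many children are affected cannot be estimated: the documents give neither the MRD-positive share nor the rate at which GVHD resolves. Because the weight of the protocol favors the stricter rule, 5.8 should be aligned to it.

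**What to change.** 1. At the head of 5.8 add: *Apart from the exception stated here, DLI under 5.8.2 to 5.8.4 is given only to patients who meet the High Risk criteria in 5.3.4. After resolved Grade 2 acute GVHD with positive MRD before or after transplant, the treating physician may choose to give DLI (5.7.6). Patients with past Grade III-IV acute GVHD or past chronic GVHD do not receive DLI.* Stating the exception once, in permissive terms, keeps it from falling under the directive wording of 5.8.2 and 5.8.4.

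2. In 5.4.2 add: *subject to the GVHD and Low Risk criteria in 5.3.4*. The Low Risk reference is needed because 5.3.4 applies that group to ALL patients whatever their chimerism.

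This is a wording amendment with no added procedures or patients. Its cost is clinical: a few MRD-positive children with past Grade III-IV or chronic GVHD would not receive DLI that 5.8 read alone would give, and section 1.1 puts survival after post-transplant relapse below 20% at 4 years. If the sponsor prefers the looser rule for that reason, it should say so and amend 5.3.4, 3.1.4 and 5.7.6 instead.
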